Product: MK-8259

Protocol/Amendment No.: 021

VEAP ID NO: 6189

Date: 15-January-2018

**THIS PROTOCOL AND ALL OF THE INFORMATION RELATING TO IT ARE
CONFIDENTIAL AND PROPRIETARY PROPERTY OF MERCK SHARP & DOHME CORP.,
A SUBSIDIARY OF MERCK & CO., INC., WHITEHOUSE STATION, NJ, U.S.A.**

SPONSOR:

MSD Pharmaceuticals LLC, a subsidiary of Merck & Co., Inc.

(hereafter referred to as the Sponsor or Merck)

[name]

[name]

TITLE:

A Prospective Observational Study to Evaluate Clinical and Radiological Manifestations of Coxitis in Patients with Ankylosing Spondylitis treated with Simponi® (golimumab)

Product: MK-8259

Protocol/Amendment No.: 021

VEAP ID NO: 6189

Date: 15-January-2018

Summary of Changes

Summary of Changes for Amendment of 15 January 2018

Protocol Section	Change
Protocol Summary	
Approximately 40 months (16 months recruitment, plus 24 months follow up with interim statistical analysis at 12 months of follow up)
 
Sample size calculation is based on data from GO-RAISE registration study in which golimumab was evaluated in patients with AS. The baseline BASFI was 5.0 which changed by mean (\pm SD, standard deviation) -2.5 (± 2.12) at week 52 (approximately 12 months). The analysis of the data shows that the minimum necessary sample size should be 18 patients to show a statistically significant change of BASFI from baseline to 12 months. On this basis and considering that the dropout rate over the two years is expected to be 30%, we decided that the necessary number of patients to be included into protocol should be 39 individuals. It is expected that around 27 patients will be included in the patient set completing the study. Power of the study is 90% with formula evaluation $P = 1 - \beta$ where P is power and β is type 2 error = 10%.

6.1.2.3 Interim Statistical Analysis	Interim Statistical Analysis will be performed when at least 18 patients recruited are observed and have their tests done at 12 months.
6.1.2.4 Central collection and evaluation of X-ray, MR Images and US protocols	Central collection and evaluation will be performed when at least 18 patients recruited are observed and have their tests done at 12 and 24 months.
8.1.1 Interim Statistical Analysis	Interim Statistical Analysis will be performed when at least 18 patients recruited are observed and have their tests done at 12 months.
8.2.1 Methods to Minimize Bias	Bias from early drop out of patients from the study can be reduced with Interim Statistical Analysis which is to be performed when at least 18 patients recruited are observed and have their tests done at 12 months. Also, patients who drop out before final follow up visit are planned to enter an analysis of last-observation-carried forward (LOCF). Data recorded on the last visits of patients will contribute to the analysis.

Product: MK-8259

Protocol/Amendment No.: 021

VEAP ID NO: 6189

Date: 15-January-2018

Protocol Section	Change
8.2.2 Limitations	
This study will collect data on patients being treated in real clinical Rheumatology practice. It is expected that the number of patients dropping out before completion of the whole course of observation will be about 30%. To minimize this limitation, the study will enroll 39 patients to ensure that the number of subjects entering the analysis Per Protocol will be enough (27 subjects). In addition, secondary analyses will evaluate data on completers vs patients dropping out before completion separately.

8.3 Sample Size and Power Calculations	
Thus, the analysis of the data shows that the minimum necessary sample size should be at least 18 patients to show a statistically significant change of BASFI from baseline to 12 months.
 
On this basis and considering that the dropout rate over the two years of the study is expected to be about 30% (ranging from 21% in a randomized controlled study [19] to 37% in real clinical practice [25]), it is decided that the necessary number of patients to be included into the study should be 39 individuals. It is expected that at least 27 patients will be included in the patient set completing the study.

11 List of References	
Manara M. et al et al. Two-year retention rate of golimumab in rheumatoid arthritis, psoriatic arthritis and ankylosing spondylitis: data from the LORHEN registry. Clinical Experimental Rheumatology, 2017 Vol.35, N°5. Pg. 0804-0809

Product: MK-8259
 Protocol/Amendment No.: 021
 VEAP ID NO: 6189
Date: 15-January-2018

Table of Contents

SUMMARY OF CHANGES	2
Summary of Changes for Amendment of 15 January 2018	2
PROTOCOL SUMMARY	7
1 BACKGROUND AND RATIONALE	8
1.1 Background.....	8
1.2 Rationale.....	11
2 OBJECTIVES	11
2.1 Primary Objective.....	11
2.2 Secondary Objectives.....	12
2.3 Exploratory objectives	12

8.3 Sample Size and Power Calculations.....	29
9 ADMINISTRATIVE AND REGULATORY DETAILS	30
9.1 CONFIDENTIALITY	30
9.1.1 Confidentiality of Data.....	30
9.1.2 Confidentiality of Subject Records	30

Product: MK-8259

Protocol/Amendment No.: 021

VEAP ID NO: 6189

Date: 15-January-2018

9.1.3 Confidentiality of Investigator Information	30
9.2 COMPLIANCE WITH FINANCIAL DISCLOSURE REQUIREMENTS.....	31
9.3 COMPLIANCE WITH LAW, AUDIT AND DEBARMENT	31
9.4 Compliance with Study Registration and Results Posting Requirements	33
9.5 Quality Management System.....	33
9.6 Data Management.....	33
10 LIST OF ABBREVIATIONS	33
11 LIST OF REFERENCES	34
12 SIGNATURES	37

Product: MK-8259

Protocol/Amendment No.: 021

VEAP ID NO: 6189

Date: 15-January-2018

PROTOCOL SUMMARY

Title	A Prospective Observational Study to Evaluate Clinical and Radiological Manifestations of Coxitis in Patients with Ankylosing Spondylitis treated with Simponi® (golimumab) – GO-COX
Vendor/Collaborator	Atlant Clinical Ltd
Rationale	Coxitis in AS is inflammation of hip(s) affecting significant number of patients. It is associated with worse function and more expressed axial disease requiring hip replacement at end-stage. Number of studies dedicated to coxitis treated with TNF alpha inhibitors is very limited. Simponi® (golimumab) has not been studied in hip disease in AS although it is registered for AS. This study will provide valuable data on clinical and radiological signs of coxitis in AS at baseline and its clinical and radiological evolution during treatment with golimumab in daily clinical practice.
Primary Objective(s)	To evaluate change of functional impairment in AS patients with coxitis from baseline to 12 months of therapy with golimumab by BASFI in daily clinical practice
Study Design	This study is a non-interventional prospective observational cohort study conducted in multiple centers across Russia.
Study Population	Patients with ankylosing spondylitis (according to the modified New York criteria) with coxitis newly prescribed golimumab during the course of usual clinical care will be enrolled and followed prospectively for 24 months with data collection at the approximate time points: baseline (pre-treatment) and consequent every 6 months.
Study Duration	Approximately 40 months (16 months recruitment, plus 24 months follow up with interim statistical analysis at 12 months of follow up)
Exposure and Outcome	Patients will receive golimumab as prescribed in regular clinical practice.
Statistical Methods	Quantitative variables will be tested for normal distribution using the Shapiro-Wilk test. The hypothesis of equality of variances will be tested using Levene's test. Quantitative variables matching a normal distribution will be described in terms of the mean \pm standard deviation, and values outside of the normal distribution as medians, 25% and 75% quartiles. Qualitative variables will be presented in the form of percentages of the absolute value N.
Sample Size and Power Calculations	Sample size calculation is based on data from GO-RAISE registration study in which golimumab was evaluated in patients with AS. The baseline BASFI was 5.0 which changed by mean (\pm SD, standard deviation) $-2.5 (\pm 2.12)$ at week 52 (approximately 12 months). The analysis of the data shows that the minimum necessary sample size should be 18 patients to show a statistically significant change of BASFI from baseline to 12 months. On this basis and considering that the dropout rate over the two years is expected to be 30%, we decided that the necessary number of patients to be included into protocol should be 39 individuals. It is expected that around 27 patients will be included in the patient set completing the study. Power of the study is 90% with formula evaluation $P = 1-\beta$ where P is power and β is type 2 error = 10%.
Limitations	In this non-interventional study the quality of the data is important. Therefore, it is important for the sponsor or designee to monitor data completion and perform quality checks during the course of the study. To minimize missing data, a set of core variables is required to be available at enrollment as part of inclusion criteria.

Product: MK-8259

Protocol/Amendment No.: 021

VEAP ID NO: 6189

Date: 15-January-2018

1 Background and Rationale

1.1 Background

Ankylosing Spondylitis (AS) is a chronic autoimmune disease characterized by back pain caused by inflammation of the sacroiliac joints and spine. In Europe, prevalence of AS ranges from 0,08% to 1,8% , while incidence is 1,5-7,3 per 100 000 depending on population studied [1,2]. In Russia, an absolute number of AS patients was reported as 39800 (approximate prevalence 0,028%) and the incidence was 5 438 patients per year (approximate incidence 3,9 per 100 000) in 2010. Also, it was noted that the number of patients is increasing. Thus, approximate prevalence was 0,022% and 0,024% in 2004 and 2008, respectively. Approximate incidence was 2,5 per 100 000 in 2006 [3].

The grow of prevalence and incidence of AS in Russia might be related to arrangement of national educational campaign across the country in 2010-2014. This campaign has been led by a Spondyloarthritis Research Taskforce of the National Research Rheumatology Institute n.a. V.A.Nosonova. MSD is one of the main sponsors of the educational campaign. Thus, MSD sponsored 20 and 18 regional spondyloarthritis schools (local conferences) in different regions of Russia in 2012 and 2013, respectively [MSD data].

Involvement of hip joint (coxitis) occurs in 24-36% of AS patients [4]. The joint can be affected by synovitis, enthesial inflammation and bone marrow involvement. The clinical pattern of coxitis includes typical inguinal pain with impaired and painful movement of the hip [9]. Coxitis is associated with more severe AS. It is recognized that patients with hip disease have worse BASFI scores than patients without hip involvement [4,5,9]. These higher BASFI scores might be associated with all BASFI questions of which many appear to be directly related to the hip (e.g. difficulty with getting up off the floor or out of a chair, tying shoes, climbing stairs) [5], but also with questions related to functions with no hip involvement (e.g. looking over the shoulder without turning your body) [4,5]. Moreover, there is clear evidence that coxitis is associated with more pronounced axial disease, clinically and radiologically: patients with clinical hip involvement are more prone to have severely limited cervical rotation [4] and patients with hip scores of 2 or greater (BASRI hip scores) have median BASRI spine scores that are more than two points higher than those of patients with a hip score of 0 [6]. Coxitis is associated with earlier beginning of AS including juvenile onset [4,7] and its longer duration [5]. The combination of the stiff spine and hip can severely affect physical status of patients and their quality of life, psychosocial status and employability [8].

Radiography, ultrasonography (US) and MRI are used to confirm clinical manifestation of coxitis in AS patients [9]. The most widely used and best validated radiological index is the bath ankylosing spondylitis radiology index (BASRI hip). In this score, the hips hip radiographs are graded on a scale of 0-4 (0 – no change; 1 – suspicious: focal joint space narrowing; 2 – mild: circumferential joint space narrowing >2mm; 3 – moderate: circumferential joint space narrowing \leq 2mm or bone-on-bone apposition of <2 cm; and 4 – severe: bone deformity or bone-on-bone apposition of \geq 2 cm) [9].

US can reveal synovial hypertrophy, synovial hypervascularization and joint effusion [9].

MRI can detect soft tissue and bone inflammation of hip. There was a recent Chinese study investigating inflammatory MRI changes in AS patients investigating pattern of hip involvement. Active inflammatory changes included subchondral bone marrow edema, joint effusion, abnormal synovial enhancement, enthesitis at sites where ligaments and tendons are attached to bone. They are visualized

Product: MK-8259

Protocol/Amendment No.: 021

VEAP ID NO: 6189

Date: 15-January-2018

best by STIR (short tau inversion recovery) sequence and fat-saturated contrast-enhanced T1-weighted sequence. Chronic inflammatory changes were fatty degeneration, erosive destruction, joint space narrowing, sclerosis, ankylosis. They are best seen by using a T1-weighted TSE sequence [10]. The proportion of hip involvement according to MR imaging, radiographs, and clinical symptoms was:

	Proportion of hip involvement
MRI	74,1% (86/116)
Radiography	20,7% (24/116)
Clinical symptoms	30,2% (35/116)

MRI yielded higher values than radiographs and clinical symptoms in the detection of hip involvement in patients with AS ($P <0.05$). The frequency of MRI changes in 81 hips (42 patients) have been shown to be: acute changes alone – 43,1%, chronic and acute changes – 26,7%, normal – 25,9%, chronic changes – 4,3%. The rates of acute MRI inflammatory changes have been shown to be:

	Rates of acute MRI inflammatory changes
Synovitis alone	48,1%
Synovitis + bone edema	21,0%
Synovitis + bone edema + enthesitis	18,5%
Synovitis + enthesitis	8,6%
Bone edema alone	3,7%
Enthesitis alone	0
Bone edema and enthesitis	0

There are no studies investigating correlation of different radiological manifestations over time.

According to current international guidelines, management of AS patients with coxitis does not differ from management of AS patients without hip involvement and includes physiotherapy, pharmacological therapy (NSAIDs, sulfasalazine, TNF alpha inhibitors) and surgery [8,11,12,13]. The latter is total hip replacement which is used in cases of end-stage disease [9]. In analysis of three databases of AS patients (Belgian database ASPECT, n=847, Spanish database REGISPOSNER, n=1405 and Ibero-American database RESPONDIA, n=466), it was shown that 5-8% of the AS patients undergo hip replacement surgery, 47% of them have bilateral hip replacement. After >30 years of disease duration, the chance of having at least one replaced hip is 12-25% [4]. Investigators who were analyzing Norwegian

Product: MK-8259

Protocol/Amendment No.: 021

VEAP ID NO: 6189

Date: 15-January-2018

Arthroplasty Register noticed that in 2003-2010 there was a trend towards a reduced frequency of hip replacement procedures in the AS group when compared to osteoarthritis group. It was hypothesized that this trend was related to broader introduction of TNF alpha inhibitors [14].

According to the ASAS/EULAR recommendations for the management of ankylosing spondylitis, anti-TNF therapy should be given to patients with persistently high disease activity despite conventional treatments [11]. Literature search identifies three publications on efficacy of TNF alpha inhibitors in hip disease in AS patients.

The first one, by Wang D. et al, describes results of follow-up in 56 patients with AS with coxitis treated with etanercept in combination with MTX. It was shown that Harris hip score, BASDAI, BASFI, ESR, CRP improved after 12 weeks of therapy ($p<0,001$ for all measurements). No radiological data were provided [15].

The second one, by Lian F. et al, presents results of 12-month treatment of coxitis in 92 AS patients with etanercept in combination with MTX. It was shown that Harris hip score, BASDAI, BASFI, ESR, CRP improved after 12 months of therapy ($p<0,05$ for all measurements). In the whole population of patients BASRI-hip remained with no changes (baseline vs. 12 month of treatment). MRI proved a total of 93 hip joints (51%) had joint fluid synovitis in MRI at baseline and 13 positive hip joint fluid synovitis at the 12th month [16]. Other MRI symptoms were not described by the authors.

The third one, by Konsta M. et al, contains results of retrospective study analyzing clinical (BASDAI, BASFI) and radiographical (BASRI hip, mean joint space width) in 23 patients being treated with infliximab for $6\pm2,5$ years (mean \pm SD). BASDAI and BASFI improved over time (from 6.3 and 6.9 to 1.67 and 3.3, respectively), while individual BASRI-hip scores at baseline (2.50 ± 0.86 , mean \pm SD) remained unchanged as well as the average width of the whole joint space in these patients (3.59 ± 0.79 mm) was not reduced at end of follow-up. Authors assume that TNF inhibitors are able to inhibit structural progression of hip disease in AS but state that prospective studies with at least 2-years follow-up are required to investigate structural progression of coxitis in AS [17].

The novel TNF alpha inhibitor Simponi® (golimumab) has sophisticatedly been studied in AS in GO-RAISE study. It was shown that golimumab provides clinical and radiological response. At week 24, ASAS 20 response was registered in 55,8% ($p<0,001$ vs. placebo) of patients taking golimumab 50 mg subcutaneously once per 4 weeks. During a 5-years follow-up, response was maintained: BASDAI at week 52 and 256 was 2.6 and 2.2, respectively (baseline BASDAI was 6.6); BASFI at week 52 and 256 was 2.5 and 2.0, respectively (baseline BASFI was 5.0). Spine MRI inflammation index (ASspiMRI-a) decreased from 9,3 at baseline by 5.9 ($p=0,011$ vs. placebo) and 7.1 at week 14 and 104, respectively [18,19,20,21]. Based on data provided by GO-RAISE study, Simponi® (golimumab) has been registered in AS and can be recommended for daily clinical practice in Russia [22]. But patients with coxitis were not included in GO-RAISE study.

In EULAR 2014, the first data from real clinical practice on Simponi® (golimumab) were presented - GO.A.RE.L. (Golimumab in Apulian real-life patients). According to the abstract, 76 patients with axial-SpA has been treated with golimumab and followed up for up to 24 months. Disease activity characteristics are presented in the table:

	BASDAI	ASDAS-CRP
--	--------	-----------

Product: MK-8259

Protocol/Amendment No.: 021

VEAP ID NO: 6189

Date: 15-January-2018

Baseline	5.9	3.9
6 months	2.76	1.6
12 months	2.96	1.9
24 months	2.32	1.5
p	0.0021	NS

These preliminary results confirmed a good effectiveness of golimumab in patients with axial SpA in standard care settings [23]. But patients with coxitis were not included in GO.A.RE.L. study.

1.2 Rationale

Coxitis in AS is inflammation of hip(s) affecting significant number of patients. It is associated with worse function and more expressed axial disease requiring hip replacement at end-stage. Clinical symptoms (pain and affected movement) should be confirmed with imaging (X-ray and MRI). Synovitis and its combination with bone edema and enthesitis are the most frequent MRI manifestations. There are no data on change of these manifestations over time with or without treatment. US imaging can reveal inflammatory changes in hips but there are no data on change of US manifestations over time.

Number of studies dedicated to coxitis treated with TNF alpha inhibitors is very limited: one of them is a retrospective study with 23 patients, two others are prospective but with short follow-up for 12 months (when at least two years are recommended as a follow-up in AS to investigate the radiographic progression) and without conclusive imaging data (MRI and/or US). Simponi® (golimumab) has not been studied in hip disease in AS although it is registered for AS.

Hip disease in ankylosing spondylitis is understudied. This study will provide valuable data on clinical and radiological signs of coxitis in AS at baseline and its clinical and radiological evolution during treatment with TNF alpha inhibitors in daily clinical practice. Collection of radiological data will include US and MRI which have not been widely explored as evaluation of coxitis in AS in previous studies.

Based on data from studies described in the Background section it can be expected that the TNF alpha inhibitor golimumab will be effective clinically and radiologically:

- 1) it is expected significant improvement of BASFI at 12 months from the baseline;
- 2) it is expected that there will be no structural progression of coxitis at 12 and 24 months from the baseline expressed as stable BASRI hip index.

2 Objectives

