3.3 Inclusion Criteria

All inclusion and exclusion criteria will be reviewed by the investigator or qualified designee to ensure that the subject qualifies for the study.

Product: MK-8259

Protocol/Amendment No.: 021

VEAP ID NO: 6189

Date: 15-January-2018

All patients need to meet all of the following inclusion criteria:

1. Adult patients (>18 years of age) with definite AS (as per modified New York criteria)
2. Coxitis with BASRI-hip score 0-2
3. Newly prescribed golimumab according to usual clinical practice
4. Naïve to anti-TNFs or other biologic agents prior to initiation of golimumab as indicated by the patient's medical records
5. Patient is enrolled after the investigator's decision to treat with golimumab, but before initiation of treatment with golimumab
6. Patient was informed of the benefits and risks of golimumab as per normal practice using the product leaflet
7. Signed informed consent form

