8.1 Statistical Methods

Quantitative variables will be tested for normal distribution using the Shapiro-Wilk test. The hypothesis of equality of variances will be tested using Levene's test. Quantitative variables matching a normal distribution will be described in terms of the mean \pm standard deviation, and values outside of the normal distribution as medians, 25% and 75% quartiles. Qualitative variables will be presented in the form of percentages of the absolute value N.

Product: MK-8259

Protocol/Amendment No.: 021

VEAP ID NO: 6189

Date: 15-January-2018

Quantitative variables that meet normal distribution criteria and equality of variances will be compared using Student's paired t-criteria. The Wilcoxon signed rank will be used to compare quantitative variables that do not meet normal distribution or equality of variance criteria.

Comparative analysis of qualitative variables will use a Chi-square test. If at least one of the absolute rates is less than 5, an exact two-sided Fischer's test is to be used.

Descriptive analysis will be used for the following:

- 1) description of the study population at the baseline;
- 2) data completeness;
- 3) distributions of reasons for discontinuation for the study population;
- 4) attrition of the study population;
- 5) durability and variability of responses.

Descriptive analysis is to be done via completion of standard tables and creation of graphical representation of each patient over time as his/her own line connecting each data point.

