8.1.3 Secondary Objectives: Calculation of Epidemiological Measures of Interest

- Change of BASFI score from baseline to 24 months of therapy
- Change of BASMI score from baseline to 12 and 24 months of therapy
- Change of ASDAS-CRP score from baseline to 12 and 24 months of therapy
- Change of BASDAI score from baseline to 12 and 24 months of therapy
- Change of BASRI-hip score from baseline to 12 and 24 months of therapy

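### Stable BASRI-hip is expected at 12 and 24 months, but no planned output gives the proportion of patients who worsen with a confidence interval, and the LOCF rule does not fit the X-ray schedule

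*Combined protocol and SAP*

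**What the plan says.** Section 1.2 sets out two expectations for golimumab. The first is BASFI improvement at 12 months. The second is that "there will be no structural progression of coxitis at 12 and 24 months from the baseline expressed as stable BASRI hip index".

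Section 2.2 makes BASRI-hip a secondary objective, and Section 8.1.3 defines the measure as "Change of BASRI-hip score from baseline to 12 and 24 months of therapy". Neither section says what counts as progression or as stability.

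Section 8.1 gives general methods. Normally distributed variables get a mean and SD and a paired t test. It describes "values outside of the normal distribution as medians, 25% and 75% quartiles". It also states: "The Wilcoxon signed rank will be used to compare quantitative variables that do not meet normal distribution or equality of variance criteria". For categories, "Comparative analysis of qualitative variables will use a Chi-square test", with Fisher's test for small counts and percentages as the summary. A plot with one line per patient is planned. No confidence interval is mentioned for BASRI-hip.

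Hip films are scheduled at baseline, 12 and 24 months, subject to availability (Sections 3.1, 4.3.6 and 5). Section 2.3 names the 6- and 18-month visits as the LOCF source when 12- or 24-month data are missing. Section 8.2.2 sends patients with missing data to LOCF and also allows the visit after the missing one to be used. Neither section mentions X-ray.

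**The concern.** A difference test asks whether the data rule out no change. Stability is the reverse question: do the data rule out a worsening large enough to matter? In a small cohort where few patients move a grade, a non-significant result and a row of zeros are to be expected whether or not some patients are progressing.

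The radiographic result is a main reason for following patients to 24 months. Sections 1.1 and 1.2 say that at least two years are needed to study structural progression. If the planned outputs are all that is reported, the 24-month finding could be summarised as no change when the data cannot exclude material worsening.

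The LOCF wording adds a smaller uncertainty: two analysts could give the same patient with a missing film different BASRI-hip values.

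**Working it through.** **Inputs.** From Section 8.3: 39 enrolled, about 30% dropout (range 21% to 37%), 27 completers, alpha 5%. From Section 3.3: "Coxitis with BASRI-hip score 0-2", so every patient has room to worsen on the 0–4 scale. The documents give no progression rate and no BASRI-hip margin.

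**The plan's own figure.** 27/0.70 = 38.6, rounded up to 39; 39 × 0.70 = 27.3. The 27 completers reproduce. At 37% and 21% dropout, 39 × 0.63 = 24.6 and 39 × 0.79 = 30.8, so about 25 to 31. The study is sized on BASFI; no figure is given for BASRI-hip.

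**Assumptions for illustration.** One-grade worsening, no improvers, a film for every completer, unchanged patients dropped from the signed-rank test.

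**Which route Section 8.1 leads to.** For 5 changes of +1 and 22 of 0, Shapiro-Wilk gives p of about 1e-8, so the summary is median and quartiles and the test is Wilcoxon.

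**Summary.** With 6 of 27 worse, 21 of 27 changes (78%) are 0, so the 25th, 50th and 75th percentiles are all 0. The quartiles therefore stay at 0 up to 6/27 = 22%.

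**Test.** With k tied positive changes each has rank (k+1)/2, and W = k(k+1)/2.
- Exact: p = 2 × 0.5^k.
- Normal approximation: mean W/2, variance k[(k+1)/2]²/4, which gives z = √k.
- Continuity-corrected: z = (W/2 − 0.5)/SD. For k = 5, (7.5 − 0.5)/3.354 = 2.09.

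| Progressors of 27 | Exact p | Corrected p | Uncorrected p |
|---|---|---|---|
| 4 | 0.125 | 0.072 | 0.046 |
| 5 | 0.0625 | 0.037 | 0.025 |
| 6 | 0.031 | 0.020 | 0.014 |

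Significance needs 6, 5 or 4 progressors respectively. Section 8.1 does not say which version will be used.

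**Chance of missing true progression, n = 27.** The number of progressors X is binomial (27, true rate). The miss probability is P(X ≤ 5) exact, P(X ≤ 4) corrected and P(X ≤ 3) uncorrected.

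| True rate | Exact | Corrected | Uncorrected |
|---|---|---|---|
| 5% | 99.8% | 99.0% | 95.6% |
| 10% | 95.3% | 87.3% | 71.8% |
| 15% | 79.0% | 61.9% | 40.7% |

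For 25 to 31 completers, the 15% row runs from 84% to 68% (exact) and from 47% to 30% (uncorrected).

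**What an interval would show.** Exact (Clopper-Pearson) 95% limits: 5/27 = 18.5%, interval 6.3% to 38.1%. For 0/27 the upper limit is 1 − 0.025^(1/27) = 12.8%; for 25 and 31 completers it is 13.7% and 11.2%.

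**LOCF against the film schedule.** A missing month-12 grade has no month-6 film to draw on. It could be filled from baseline (zero change by construction), filled from month 24 under the next-visit wording in Section 8.2.2, or left missing. With constant dropout d over two years, losses before month 12 are 39 × (1 − √(1−d)): 4.3, 6.4 and 8.0 patients at 21%, 30% and 37%. If a proportion were reported and all 12 dropouts were given zero change (an extreme case), 5/27 = 18.5% would become 5/39 = 12.8%. The zero-event upper limit would fall from 12.8% to 1 − 0.025^(1/39) = 9.0% with no new data.

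**The case against.** Stability is an expectation in the rationale, not a planned test. The stated objective is to evaluate change, and a change score with a difference test answers it. A reader might infer that the plan will declare stability from p > 0.05. No section says so; the risk is one of interpretation that the plan leaves open.

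The outputs are also wider than medians and quartiles. With about 27 patients, the line plot would show anyone who worsens. That stands in part. A plot is not a prespecified count with an interval, and grade percentages at each visit show only the net shift, in which worseners and improvers offset.

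A reader might infer that 5 progressors of 27 would certainly go undetected. That holds only for the exact test; both approximations are significant. The same is true of 7 worsening against 1 improving: p = 0.070 exact, 0.034 to 0.041 approximate.

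Progression may be rare. Section 1.1 reports of a 92-patient cohort over 12 months: "In the whole population of patients BASRI-hip remained with no changes". Of a 23-patient cohort followed for about 6 years it says that hip scores "remained unchanged as well as the average width of the whole joint space in these patients" were not reduced. Read as 0 of 92 and 0 of 23, these still allow 1 − 0.025^(1/92) = 3.9% and 1 − 0.025^(1/23) = 14.8%. Neither cohort received golimumab. The first statement is for the population as a whole, and the second cohort's mean baseline grade of 2.50 exceeds the maximum of 2 allowed here.

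On LOCF, a reader might infer that carrying values forward will hide progression in the planned results. The documents do not support that. Carrying zeros forward leaves the signed-rank test unchanged and the median and quartiles at 0 in these examples; the dilution applies to a proportion, which the plan does not report. Section 3.1 also says unavailable data are reported as missing, though in a paragraph that opens with baseline data. The ambiguity is real, but its effect on the planned outputs is small.

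**Conclusion.** The point holds as an improvement to a secondary outcome. The planned BASRI-hip outputs can show whether change is detectable, but they cannot support the stability expected in Section 1.2, because none gives the proportion worsened with an interval. At the planned size a true 10% progression rate would give a non-significant test between 72% and 95% of the time, depending on an algorithm the plan leaves open.

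These figures rest on assumed progression rates, one-grade changes, no improvers and complete films among completers. They show what the design can and cannot exclude; they do not predict that patients will progress. The lack of fit between the LOCF rule and the film schedule is a separate, smaller matter needing one clarifying sentence. In a single-arm study no interval can attribute stability to treatment.

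**What to change.** Amend Section 8.1.3 as follows.
- Report, at 12 and 24 months, the number and proportion of patients whose BASRI-hip worsens by at least one grade, with an exact 95% confidence interval. State in advance how a patient's two hips are combined.
- Give beside it the number with paired films and the number who improve, as a guide to reading error.
- Use observed films only, centrally read where available (Section 6.1.2.4).
- State that neither LOCF nor the next-visit rule applies to BASRI-hip.
- Word any stability statement by the upper confidence limit, not by p > 0.05.

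Optionally, add best- and worst-case bounds for missing films. They will be wide: 1 progressor among 27 films becomes 1/39 = 2.6% to (1 + 12)/39 = 33.3%.

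The cost is a text amendment to Section 8 of the protocol; no films, visits or patients are added. The headline will be less favourable, since even zero progressors in 27 leaves 12.8% open. Observed films may favour stability if patients who drop out progress more. Some one-grade changes will be reading error, more so if worsening in either hip counts.
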